2.1.1.8 Method for calculating Confidence Intervals

95% confidence intervals for proportions will be calculated using the exact (Clopper-Pearson) method, unless stated otherwise.

95% confidence intervals for change and percentage change from baseline will assume normally distributed data and will be calculated using the t-distribution.

2.1.1.9 AE summary cutoff

All data up to data cut-off date will be at least listed. All safety data prior to the data cut-off will be summarized with the exception of AEs and deaths, which will follow the cut-off rule specified below.

AE/death summary cut-off date = min { data cut-off date, max(last dosing date + 30 , safety follow-up visit date) }

AEs/deaths that occur after the AE/death summary cut-off date but prior to the data cut-off date will be listed and flagged.

2.1.1.10 Criteria of adequate follow-up for time points in the extension period

For a given time point in the extension period, it will be considered to have adequate follow-up to be included in the reporting activities if there are at least 15 patients available for the analysis at that time point.

2.2 Analysis sets

Full analysis set (FAS): comprises all enrolled patients who receive at least one dose of LCI699. FAS is used in efficacy analysis for study period other than RW period including key secondary endpoint.

Safety set (SAS): comprises all enrolled patients who received at least one dose of LCI699 and had at least one valid post-baseline safety assessment. Please note: the statement that a patient had no adverse events (on the Adverse Event CRF) constitutes a safety assessment.

Per-Protocol set: There are two per-protocol sets defined in this study.

- The Per-Protocol Set for Randomized Analysis Set (PPRAS) consists of a subset of the patients in the RAS who had no selected protocol deviations.
- The Per-Protocol Set for Full Analysis Set (PPFAS) consists of a subset of the patients in the FAS who had no selected protocol deviations.

PPFAS will only be used in supportive analyses for key secondary efficacy endpoint, while PPRAS will only be used in supportive analyses for primary efficacy endpoint. Details of protocol deviations that lead to exclusion from PPS and/or PPRAS can be found in table below.

Table 2-3 Protocol deviations leading to exclusion from PPFAS and/or PPRAS

Protocol Deviation description	Protocol deviation Code(s) in VAP3 (Amendment 4, July2017)	Excluded from PPFAS?	Excluded from PPRAS?
Informed consent for core phase not documented	I01	Yes	Yes
mUFC related inclusion criteria not met	I06/I07	Yes	Yes
ACTH related inclusion criteria not met	I09	Yes	Yes
Cushing's disease confirmation is missing	I10	Yes	Yes
Pituitary surgery related inclusion criteria not met	I11/I12	Yes	Yes
Pituitary irradiation related inclusion criteria not met	I14	Yes	Yes
Washout period related inclusion criteria not met	I13/I15/I16/I17/I18/I19/I20	Yes	Yes

Subject did not meet the eligibility criteria for randomization but was randomized at Week 26.	I21	No	Yes
Participation in another trial with an investigational drug does meet the exclusion criteria	E01	Yes	Yes
Subject pregnant or lactating at study entry	E04/E05	Yes	Yes
Subject's history of hormone over secretion does meet the exclusion criteria	E10	Yes	Yes
Subject's medical history of Cushing's syndrome does meet the exclusion criteria	E11	Yes	Yes
Subject compliance history does meet the exclusion criteria	E23	Yes	Yes
Subject met the discontinuation criteria, but was not discontinued from study treatment	D01/D02	Yes*	Yes**
Subject took a prohibited concomitant medication	M01	Yes*	Yes**

*If protocol deviation happens before Week 24, when the key secondary endpoint is assessed

**If protocol deviation happens before end of randomized withdrawal period, when the primary endpoint is assessed

The analysis sets used for various analyses in the Final CSR are summarized below

Table 2-4 Analysis sets used for specific analyses

	FAS	SAS	PPFAS/ PPRAS
Patient Disposition	X		
Demography and baseline disease characteristics	X		
Medical History	X		
Prior Medication	X		
Protocol Deviation	X		
Concomitant Medications		X	
Exposure to study medication		X	
Efficacy analyses	X		X*
Safety analyses		X	
Patient-reported outcomes	X		
* PPFAS will only be used in supportive analyses for key secondary efficacy endpoint. * PPRAS will only be used in supportive analyses for primary efficacy endpoint.			

When appropriate, patients in a given analysis set could be classified into mutually exclusive treatment groups as described below:

For patients in PPRAS

- LCI699 group: patients randomized to continued treatment of LCI699 for the randomized withdrawal period of the study
- Placebo group: patients randomized to placebo for the randomized withdrawal period of the study

For patients in FAS/PPFAS

- LCI699 group: patients randomized to continued treatment of LCI699 for the randomized withdrawal period of the study
- Placebo group: patients randomized to placebo for the randomized withdrawal period of the study
- Non-randomized patients: patients who do not enter randomized withdrawal period of the study (either discontinued study before the randomization or not eligible to be randomized)

For patients in SAS

- LCI699 group: patients receiving study treatment of LCI699 for the randomized withdrawal period of the study
- Placebo group: patients receiving study treatment of placebo for the randomized withdrawal period of the study
- Non-randomized patients: patients who do not enter randomized withdrawal period of the study (either discontinued study before the randomization or not eligible to be randomized)

2.2.1 Subgroup of interest

Subgroups of interest for this study include the two stratification factors for randomization

History of pituitary irradiation: Yes and No

LCI699 dose at Week24: $\leq 5\text{mg b.i.d.}$ and $> 5\text{mg b.i.d.}$

For the Final CSR, the per-protocol analysis of the primary efficacy endpoint will be performed including adjustment for the two stratification factors.

2.3 Patient disposition, demographics and other baseline characteristics

Summary statistics of data pertaining to subject disposition, demographics, baseline characteristics, medical history, prior medications and protocol deviations will be tabulated and displayed using grouping described in Section [2.2](#).

2.3.1 Patient disposition

For overall study period, counts of patients for the following items will be summarized by treatment group using FAS:

- discontinued at any time*
- Primary reason for discontinuation at any time

- discontinued at or prior to Week 12
- Primary reason for discontinuation at or prior to Week 12
- discontinued at or prior to Week 24 but after Week 12
- Primary reason for discontinuation at or prior to Week 24 but after Week 12
- discontinued prior to Week 48 but after Week 24
- Primary reason for discontinuation prior to Week 48 but after Week 24
- Completed Week 48
 - Completed Week 48 and did not enter Extension period
 - Completed Week 48 and enter Extension period
- Ongoing in Extension
- Discontinuation in the Extension
- Primary reason for discontinuation in the Extension
- Discontinued at or prior to Week 72 but after Week 48
- Discontinued prior to Week 96 but after Week 72
- Discontinued after Week 96
- Completed extension

* Patients who completed Week 48 and declined to enter optional extension period are not counted as discontinuations.

For randomized withdrawal period, counts of patients for the following items will be provided in a separate disposition summaries presented by treatment group using RAS:

- discontinued from randomized treatment before completing RW period
- primary reason for discontinuation before completing RW period
- discontinued from randomized treatment at or prior to Week 28
- primary reason for discontinuation at or prior to Week 28
- discontinued from randomized treatment at or prior to Week 30 but after Week 28
- primary reason for discontinuation at or prior to Week 30 but after Week 28
- discontinued from randomized treatment at or prior to Week 32 but after Week 30
- primary reason for discontinuation at or prior to Week 32 but after Week 30
- discontinued from randomized treatment at or prior to Week 34 but after Week 32
- primary reason for discontinuation at or prior to Week 34 but after Week 32
- Completed the RW period (Week 34)

2.3.2 Demographic and baseline disease characteristics

All demographic and baseline disease characteristics were summarized in the interim CSR. They will not be reported in the Final CSR.

2.3.3 Medical history

Relevant medical history and ongoing medical conditions were summarized in the interim CSR. They will not be reported in the Final CSR.

2.3.4 Protocol deviations

The number and percentage of patients with any PDs up to data cutoff will be tabulated by treatment group using FAS.

PDs leading to exclusion from the PPFAS and PPRAS will be tabulated by treatment group using FAS and RAS respectively.

All PDs up to data cutoff will be listed.

The criteria for protocol deviation are specified in Validation and Planning (VAP) Module 3 and will be finalized prior to database lock.

2.4 Treatments (study treatment, rescue medication, concomitant therapies, compliance)

2.4.1 Study treatment / compliance

In the Final CSR the exposure to the study drug will be summarized for the overall study period only, using the SAS.

Duration of exposure

• For overall study period, duration of exposure to LCI699 for patients in the SAS is calculated as below:

•for Placebo group:

Duration of exposure (weeks) = (min (date of last administration of study medication, date of data cut-off, date of death) – date of first administration of LCI699 + 1)/7 – Duration of exposure to Placebo

•for LCI group and non-randomized patients

Duration of exposure (weeks) = (min (date of last administration of LCI699, date of data cut-off, date of death) – date of first administration of LCI699 + 1)/7

The above duration calculation includes the periods of temporary interruption.

Dose reduction/interruption

The number of patient who has at least one dose reductions or interruptions, and the corresponding reasons will be summarized by study period. Although patients may have multiple dose reduction or interruption with the same reason, patient will be counted only once for each distinct reason.

The actual and planned doses administered and reason for dose change will be listed with UFC information.

Dose of LCI699

The LCI699 average total daily dose by visit during the overall study period will be summarized using descriptive statistics and displayed graphically. Dose levels whilst on placebo, for patients randomized to placebo during the RW period, will not be included in the calculations.

2.4.2 Prior, concomitant and post therapies

Concomitant therapy is defined as all interventions (therapeutic treatments and procedures) other than the study treatment administered to a patient coinciding with the study treatment period. Concomitant therapy include medications (other than study drugs) starting on or after the start date of study treatment or medications starting prior to the start date of study treatment and continuing after the start date of study treatment.

Concomitant medications will be coded using the World Health Organization (WHO) Drug Reference Listing (DRL) dictionary that employs the WHO Anatomical Therapeutic Chemical (ATC) classification system. Surgical and medical procedures will be coded using MedDRA and summarized by SOC and preferred term.

Concomitant medications and significant non-drug therapies will be listed and summarized using frequency counts and percentages by ATC class, preferred term and treatment group within each of three study periods: first 26 weeks (FAS), randomized withdrawal period (RAS), and overall study period (FAS).

Therapies for Cushing's Disease taken prior to first dose of LCI699 will be summarized using frequency counts and percentages by ATC class, preferred term and treatment group.

If the start date of a concomitant medication is missing or partially missing, then it will be imputed following Novartis standard rule for table and listing.

2.5 Analysis of the primary objective

The primary objective was to compare the complete response rates at the end of the 8 weeks period of randomized withdrawal (Week 34) between patients randomized to continued LCI699 therapy vs. placebo.

The primary efficacy variable is the proportion of randomized patients in each treatment arm that are complete responders at the end of the 8 weeks of the randomized withdrawal period (Week 34). A complete responder is defined as a patient who has $mUFC \leq ULN$ (based on central laboratory result) at Week 34 and who was neither discontinued nor had LCI699 dose increase above the level at week 26 during the randomized withdrawal period of the study. Patients who discontinued during the randomized withdrawal period will be counted as non-responders for the primary endpoint. Dose reductions and temporary dose interruptions for safety reason during randomized withdrawal period do not preclude patients from being complete responder for primary endpoint.

For the primary objective, the statistical null hypothesis states that the complete response rates at the end of 8-week randomized withdrawal period (i.e., at Week 34) are the same between the two randomized arms. To test this hypothesis, a Cochran–Mantel–Haenszel exact test stratified by the two stratification factors considered for randomization will be performed using the RAS following the intent-to-treat principle.

If the 2-sided p-value is ≤ 0.05 and the odds ratio (LCI699 vs. Placebo) is > 1 , the null hypothesis will be rejected and the complete response rate in the LCI699 arm will be considered higher than that in the placebo arm.

As a supportive analysis to this analysis, 1) an un-stratified Fisher's exact test of the primary endpoint will also be performed using RAS; 2) both stratified CMH exact test and un-stratified Fisher's exact test of the primary endpoint will be performed using PPRAS.

After the interim CSR was published, additional protocol deviations were reported which affect the per-protocol population used to perform the per-protocol analyses of the primary endpoint, therefore the Final CSR will report the updated result of the supportive analyses using the PPRAS.

The analyses of the primary endpoint using the RAS are not impacted by these additional protocol deviations, and therefore will not be reported in the Final CSR.

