- LCI699 dose is maintained if the mUFC value is in the **normal range** and the patient does **not** have signs or symptoms of hypocortisolism or adrenal insufficiency.
- LCI699 dose is reduced if the mUFC value is **< LLN OR** the patient has signs and symptoms of **hypocortisolism or adrenal insufficiency** and the mUFC value is in the **lower part of the normal range**.
- **Dose reductions and temporary dose interruptions** for **safety** reasons are **permitted at any time** during the study.

Refer to [Section 6.1.1](#) for additional details.

4.1.2 Study Period 2

This period (Week 13 to Week 24) aims to assess the efficacy and safety of LCI699 at the therapeutic dose determined during the dose titration period.

Patients whose mUFC becomes elevated during this period can have their LCI699 dose increased further, if it is tolerated and the maximum dose of 30 mg b.i.d. has not been reached. Such patients will be followed for long-term safety but will not be considered complete responders, and cannot be randomized. Decreases or temporary interruptions in the dose of LCI699 for safety reasons are permitted during this period without affecting eligibility for randomization.

Dose adjustments may be managed via a phone call between visits or via an unscheduled visit at the site. Please refer to [Section 6.1.1](#) for details.

In order for a patient to be assessed as a complete responder at Week 24, the following two conditions must be met:

- $mUFC \leq ULN$ based on urine samples collected at Week 24
- The dose of LCI699 during Study Period 2 (Weeks 13-24) was not increased above the level established at the end of Study Period 1 (Week 12; end of individual dose titration period)

Dose reductions and temporary dose interruptions for reasons of safety do not preclude the possibility of complete response assessment at Week 24.

The key secondary endpoint, the proportion of patients with a complete response (mUFC \leq ULN), is assessed at Week 24.

Patients remain on open-label LCI699 during the period between week 24 and week 26, in order to ensure that sufficient time is allowed for central laboratory results (Week 24 mUFC) to become available for all patients at all sites, and to standardize the time of randomization across sites.

4.1.3 Study Period 3

Study Period 3 is a double-blind, placebo-controlled randomized withdrawal period (Week 26 to Week 34).

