4.1.3.4 UFC monitoring during randomized withdrawal

During the 8-week randomized withdrawal study period, mUFC is measured at scheduled visits every 2 weeks. However, patients are also allowed to have unscheduled visits at any time during the randomized withdrawal period if they report symptoms of hypercortisolism or hypocortisolism. The investigator decides the dose of study drug (LCI699 or placebo) during this period, although is blinded to treatment assignment. All laboratory tests during the randomized withdrawal period must be sent to the central laboratory for analysis, and all treatment decisions must be based on central laboratory results.

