4.1.3.6 Discontinuation from randomized withdrawal

During the randomized withdrawal study period, the patient must be discontinued from the randomized withdrawal period, declared a non-responder, if the mUFC increases to $> 1.5 \times$ ULN, and at least 2 individual urine samples show UFC $> 1.5 \times$ ULN at a single visit (scheduled or unscheduled).

After discontinuation from randomized withdrawal, or at the end of the randomized withdrawal period (Week 34), whichever comes first, the patient resumes open-label LCI699 at a dose selected by the investigator.

Patients who are discontinued from the study for reasons other than those described above during the randomized withdrawal period are no longer in the study, and consequently they are not permitted to receive open-label LCI699 and cannot move forward to Study Period 4.

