4.1.3.8 Complete response and primary endpoint assessment

In order for a patient to be assessed as a complete responder at Week 34, all of the following conditions must be met:

- $mUFC \leq ULN$ at Week 34
- Patient was not discontinued during the randomized withdrawal period

The primary endpoint is assessed on the basis of mUFC results at the end of the randomized withdrawal period (Week 34) for all randomized patients. The endpoint compares the complete response rate (proportion of patients with $mUFC \leq ULN$) at the end of 8 weeks of randomized withdrawal (at Week 34) between patients randomized to continued LCI699 therapy vs. placebo. Patients who are discontinued during the randomized withdrawal period are not considered complete responders.

4.1.4 Study Period 4

Study Period 4 is a single-arm, open-label therapy (Week 35 to Week 48). At the end of Week 34, all patients receive open-label LCI699 treatment. The investigator has the discretion to select the dose during this period and is advised to consider the guidelines mentioned in [Section](#)

4.1.3.7. Once the patient is on open-label LCI699, the dose may remain unchanged, increased, decreased or withheld, depending on the mUFC level, and whether or not there is an AE requiring temporary interruption of study drug. Particularly during the first few weeks of open-label LCI699 treatment (after randomized withdrawal), patients may have unscheduled visits if they report symptoms of continuing hypercortisolism, glucocorticoid withdrawal, hypocortisolism, or any adverse event.

Dose adjustments may be managed via a phone call or via an unscheduled visit at the site. Please refer to [Section 6.1.1](#) for details.

Patients continue open-label therapy until Week 48. At Week 48, patients have the option to enter an extension period or discontinue LCI699 at week 48 to conclude with an end of core study visit 4 weeks off study drug (at Week 52).

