10.4.1 Variable

The primary efficacy variable is the proportion of randomized patients in each treatment arm that are complete responders at the end of the 8 weeks of the randomized withdrawal period (Week 34). A complete responder is defined as a patient who has $mUFC \leq ULN$ (based on central laboratory result) at Week 34 and was neither discontinued nor had LCI699 dose increase above the level at week 26 during the randomized withdrawal period of the study.

Patients who discontinued during the randomized withdrawal period will be counted as non-responders for the primary endpoint. Dose reductions and temporary dose interruptions for safety reason during randomized withdrawal period do not preclude patients from being complete responder for primary endpoint.

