10.4.3 Handling of missing values/censoring/discontinuations

The mUFC will be determined at a central laboratory from three 24-hour urine specimens collected within 7 days from scheduled visit date. The mean of the results from the 3 samples will be used to obtain the corresponding mUFC level for a given assessment. If a patient has two or more missing UFC values for a particular visit, the mUFC assessment for that patient at that visit will be considered missing. Otherwise, the mean of UFC collections will be considered as the mUFC level for that visit.

Randomized patients who discontinued during the randomized withdrawal period or had a missing mUFC assessment at end of the randomized withdrawal period (Week 34) will be counted as non-responders for the primary endpoint.

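### The primary endpoint tests whether an exit took place, not whether the 1.5 x ULN non-response criterion was met, so a patient who met it but was never exited can count as a complete responder

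*SAP*

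**What the plan says.** **The non-response rule.** Protocol 4.1.3.6 states that "the patient must be discontinued from the randomized withdrawal period, declared a non-responder, if the mUFC increases to" more than 1.5 x ULN, with at least two individual samples also above 1.5 x ULN at a single visit, scheduled or unscheduled. SAP 1.2.3 repeats this.

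**The endpoint definition.** Protocol 4.1.3.8 requires Week 34 mUFC at or below ULN and "Patient was not discontinued during the randomized withdrawal period". Protocol 10.4.1 and SAP 2.5 add a condition on dose: in SAP 2.5 the responder is a patient with Week 34 mUFC at or below ULN "who was neither discontinued nor had LCI699 dose increase above the level at week 26 during the randomized withdrawal period of the study". Protocol 10.4.1 also says "Patients who discontinued during the randomized withdrawal period will be counted as non-responders for the primary endpoint". Protocol 10.4.3 adds a missing Week 34 mUFC as non-response. None of these sections tests whether the 1.5 x ULN criterion was met.

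**Timing.** Under 4.1.3.4, "mUFC is measured at scheduled visits every 2 weeks", and treatment decisions must rest on central laboratory results. Protocol 4.1.2 keeps patients on open-label drug from Week 24 to Week 26 "in order to ensure that sufficient time is allowed for central laboratory results (Week 24 mUFC) to become available", and also to standardize the time of randomization.

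**Per-protocol set.** SAP Table 2-3 excludes from PPRAS, under codes D01/D02, the deviation "Subject met the discontinuation criteria, but was not discontinued from study treatment" when it occurs before the end of the randomized withdrawal period.

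**The concern.** The protocol attaches non-response to a laboratory finding, whereas the analysis attaches it to a disposition record. The two agree whenever the exit follows the finding. They part when the finding is made and no exit happens before the period closes, either because the central result arrives too late or because the site misses the rule. If Week 34 mUFC is then normal, two patients with identical urine results can be scored differently according to laboratory turnaround or site conduct.

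At stake are the reported response rates on the primary endpoint and the PPRAS re-run that the Final CSR will contain. The per-protocol exclusion does not repair this: if it applies, it removes the patient instead of counting a failure.

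**Working it through.** **1. The two rules on one record.** Take an illustrative patient with Week 32 samples of 1.7, 1.6 and 2.1 x ULN. The mean is (1.7 + 1.6 + 2.1)/3 = 1.8 x ULN, and all three values exceed 1.5. The result arrives after the Week 34 visit, no exit is recorded, the dose is not raised, and Week 34 mUFC is 0.9 x ULN.

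| Rule | Outcome |
|---|---|
| Protocol 4.1.3.6, SAP 1.2.3 | Non-responder |
| Protocol 4.1.3.8, 10.4.1, 10.4.3, SAP 2.5 | Complete responder |

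**2. When the rules differ.** Three things must coincide: the criterion is met between the first randomized dose and Week 34, there is no exit before the period ends, and Week 34 mUFC is at or below ULN without a dose increase. An exit carried out late but inside the period is non-response under both rules. So is a missed exit with Week 34 mUFC above ULN. Meeting the criterion at Week 34 itself already fails the ULN condition, so only Weeks 28, 30 and 32 and unscheduled visits matter.

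**3. The plan's power figure.** Inputs from protocol 10.8: 70% vs 30%, 33 per arm, two-sided 0.05. With continuity correction:
- null SE = sqrt(0.5 x 0.5 x 2/33) = 0.1231
- alternative SE = sqrt((0.21 + 0.21)/33) = 0.1128
- z = (0.40 - 1/33 - 1.96 x 0.1231)/0.1128 = 1.14, so power = 87%

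The stated 87% reproduces, and this point does not challenge it.

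**4. Frequency (assumed).** The documents give none. I simulated three lognormal samples per visit under these assumptions: single-sample CV 30-50%, visit-to-visit log-SD 0.2-0.4, between-patient log-SD 0.5, and a patient level that is constant over the period. I counted patients who first met the criterion at Week 32 and had Week 34 mUFC at or below ULN, taking every Week 32 result as too late to act on.

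| Group median mUFC | Share affected | Patients per arm of 33 |
|---|---|---|
| 0.5 x ULN | about 0.3-1.8% | 0.1-0.6 |
| 1.0 x ULN | about 0.9-3% | 0.3-1.0 |
| 1.5 x ULN | about 0.8-2.3% | 0.3-0.8 |

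Requiring Week 24 mUFC at or below ULN, as eligibility does, gives about 0.2-1.4% in the first row. The extreme case, with no exit carried out at any visit, gives about 1-6%, 3-13% and 3-11%.

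**5. Effect on the result.** One patient is 1/33 = 3.0 points. The planning counts are 0.7 x 33, about 23, and 0.3 x 33, about 10. Unstratified Fisher p-values are:

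| Rescored as non-responders | Counts | p |
|---|---|---|
| None | 23/33 vs 10/33 | 0.0028 |
| 1 on LCI699 | 22 vs 10 | 0.0063 |
| 2 on LCI699 | 21 vs 10 | 0.013 |
| 3 on LCI699 | 20 vs 10 | 0.025 |
| 4 on LCI699 | 19 vs 10 | 0.046 |
| 5 on LCI699 | 18 vs 10 | 0.080 |
| 1 on placebo | 23 vs 9 | 0.0012 |

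Five rescorings, all on LCI699, would be needed to cross 0.05. Rescoring on placebo strengthens the contrast.

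**The case against.** **The SAP already carries the rule.** SAP 1.2.3 assigns non-response on meeting the criterion, and a reader who takes it together with 2.5 would score the patient as a failure. The intent is indeed clear. But 2.5 is the definition that will be programmed, it is complete on its face, and it gives the other answer.

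**Late results are not presented as normal.** Protocol 4.1.1 and 6.1.1 expect results and dose changes between visits, and the two weeks in 4.1.2 also serve to standardize randomization. This stands: two weeks is an outer margin. It equals the visit interval, however, so a late Week 32 result is possible without any misconduct.

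**The remedy comes late.** SAP 1.2.3 dates the core database lock and unblinding to 10-May-2018. SAP 2.5 says the RAS analysis will not be repeated in the Final CSR. SAP section 1 refers the core analysis to a separate SAP, cover date 06-Jul-2018, which is not in hand and may contain the missing condition. This also stands, and it rules out rewriting the primary endpoint now.

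**The per-protocol point is conditional.** D01/D02 concern discontinuation from study treatment. The 1.5 x ULN rule is an exit from one period to open-label LCI699 and is absent from the list in protocol 7.1.5. Whether the codes cover it is unclear.

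A reader might infer that any delayed exit is scored as a response, or that the primary result is biased towards LCI699. The documents support neither. Exits inside the period are counted as failures, and nothing shows in which arm the affected patients would fall.

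**Conclusion.** The inconsistency is real and narrow. Two sections make the laboratory criterion a non-response, and every operative definition of the endpoint omits it. It affects only patients who met the criterion, were not exited before the period ended and were at or below ULN at Week 34. If every exit was timely, the definitions agree and nothing changes.

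The likely size is small: about 0.3-3% of patients for a criterion first met at Week 32, or at most about one patient per arm of 33. That range rests on assumed variability, on a constant patient level and on every Week 32 result being late. Widespread failure to carry out exits would raise it, but the documents give no sign of that. At the planning counts the effect is on the reported rate rather than on significance. The point is worth acting on because the answer can be read from data already held.

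**What to change.** Reconcile protocol 4.1.3.6 and SAP 1.2.3 with 4.1.3.8, 10.4.1, 10.4.3 and SAP 2.5. Derive non-response from the central UFC data, whatever the disposition record says: the criterion met on any urine collected after the first randomized dose and up to Week 34. If the core-phase SAP already does this, cite it.

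Because the core data are unblinded, leave the reported primary analysis as it is and add to the Final CSR:
1. the number of patients, by arm, who met the criterion without being exited, with their Week 34 status;
2. a sensitivity analysis of the primary endpoint in the RAS, labelled as added after unblinding, with these patients scored as non-responders;
3. for the PPRAS re-run, a statement of whether D01/D02 covers this exit and, if it does, the result also shown with these patients kept as non-responders when this is their only deviation.

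The cost is a short derivation. SAP 2.7.7 already applies the same threshold for time-to-escape, and the PPRAS analyses are being rerun anyway. No new data are needed and the clinical exit rule does not change. The downside is that either arm's response rate may fall slightly.
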